4.1 Definitions

An adverse event (AE) is defined as any untoward medical occurrence in a subject in the investigation. AEs must be assessed for expectedness, severity, attribution (relatedness to the study intervention), and seriousness by the investigator, or another qualified study team member as characterized below. AEs deemed related to the intervention must be reported as serious adverse events (SAEs) if they become serious (become life-threatening, result in death, or prolong hospitalization). Recording of such adverse events will start at the time of the study intervention (2 weeks of age) and will stop at 36 weeks PMA or transfer/discharge (whichever occurs later).

The following criteria will be used to define relatedness:

Definite: The AE is clearly related to the study intervention

Probable: The AE is likely related to the study intervention

Possible: The AE may be related to the study intervention

Unrelated: The AE is clearly not related to the study intervention

The severity of AEs will be described as:

Mild: asymptomatic or mild symptoms, no intervention indicated

Moderate: clinically significant requiring minimal noninvasive intervention

Severe: severe or medically significant but not immediately life-threatening, need for intensive, emergent, or invasive intervention

Life-threatening: life-threatening physiological consequences, need for intensive or emergent invasive intervention

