4.2 Adverse Event Monitoring and Reporting

Extremely preterm infants commonly have multiple clinical complications and laboratory abnormalities associated with prematurity. Those listed as secondary outcomes will be collected in the REDCap database and reviewed monthly by the Study Team.

Published data involving this population and at the dose of sodium supplementation to be provided in this study have not shown any harmful effects, including hypernatremia, suggesting

this risk is minimal [33, 43]. In this patient population per routine standard of care, serum [Na] concentrations are checked daily to several times/week on infants receiving majority of intake parenterally and twice weekly to weekly for infants receiving primarily enteral intake. As this is a pragmatic, unmasked study evaluating an algorithm to assist clinicians in preventing total body sodium deficiency, AE reporting will specifically focus on states of sodium inadequacy or excess, and any additional adverse event monitoring the DSMC requests.

Adverse event monitoring will include:

Hyponatremia: mild [Na] 134-130; moderate [Na] 129-125; severe [Na] <125 Hypernatremia: mild [Na] 146-150; moderate [Na] 151-155; severe [Na] >155

(To be considered an AE, 2 consecutive measurements of hyper/hyponatremia will be required to rule out laboratory measurement variation.)

Common complications of prematurity that are not considered AE's will be collected and included in a Note to File for each participant.

Other events classified as serious and unexpected

Other events resulting in death or classified as a Serious or Related (to study procedures). All SAEs and AEs reported during this study will be followed until resolution or until the investigator confirms that the AE/SAE has stabilized and no more follow-up is required.

All deaths and serious adverse events SAEs that are at least possibly related and all unexpected SAEs will be reported to the Chair of the DSMC within 72 hours of awareness. An initial SAE form must be as complete as possible, including details of the current serious adverse event, including an Investigator assessment of the causal relationship between the event and study procedures. Information not available at the time of the initial report must be documented on a follow-up SAE form.

All AEs/SAEs that meet IU HRPP Policy on Reportable Events will be reported to the IRB within 5 working days.

SECTION 5. SAFETY, DATA MANAGEMENT, AND ANALYTICAL PLAN

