5.3 DATA SAFETY AND MONITORING PLAN

A Data Safety and Monitoring Committee (DSMC), headed by [name], Professor of Pediatrics, University of Iowa Carver College of Medicine will monitor the progress of the study when 25%, 50% and 75% of the trial subjects have reached hospital discharge. [name], who has extensive experience with DSMCs, will be responsible for recruiting the necessary individuals with expertise in neonatology, biostatistics, bioethics and clinical trials to establish the DSMC. The DSMC will review accumulated blinded study data to ensure that the intervention is not leading to harm. If there is a significant imbalance of secondary outcome rates between the study arms, the proper course of action will be discussed by the study PIs and the DSMC. The DSMC will not be charged with assessing efficacy before conclusion of the trial; therefore, no loss of alpha will result from the planned interim safety analyses.

Safety outcomes include incidence of mortality up through 36 weeks PMA, BPD, and ROP. The DSMC may request other outcomes at their prerogative. The DSMC will examine other safety outcomes, including all reported deaths and serious adverse events by treatment group in considering a recommendation to suspend the trial for safety reasons.

SECTION 5. REFERENCES

- 1. Fenton, T.R. and J.H. Kim, A systematic review and meta-analysis to revise the Fenton growth chart for preterm infants. BMC Pediatr, 2013. **13**: p. 59.
- 2. Griffin, I.J., et al., *Postnatal growth failure in very low birthweight infants born between 2005 and 2012.* Arch Dis Child Fetal Neonatal Ed, 2016. **101**(1): p. F50-5.
- 3. Horbar, J.D., et al., Weight Growth Velocity and Postnatal Growth Failure in Infants 501 to 1500 Grams: 2000-2013. Pediatrics, 2015. **136**(1): p. e84-92.
- 4. Ehrenkranz, R.A., et al., *Growth in the neonatal intensive care unit influences neurodevelopmental and growth outcomes of extremely low birth weight infants.* Pediatrics, 2006. **117**(4): p. 1253-61.
- 5. Ehrenkranz, R.A., et al., Longitudinal growth of hospitalized very low birth weight infants. Pediatrics, 1999. **104**(2 Pt 1): p. 280-9.
- 6. Franz, A.R., et al., *Intrauterine, early neonatal, and postdischarge growth and neurodevelopmental outcome at 5.4 years in extremely preterm infants after intensive neonatal nutritional support.* Pediatrics, 2009. **123**(1): p. e101-9.

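### Sections 4.1 and 4.2 conflict on whether an SAE depends on relatedness, so part of the DSMC's by-arm SAE comparison can turn on unmasked attribution

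*Combined protocol and SAP*

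**What the plan says.** Section 4.1 defines an adverse event broadly: "An adverse event (AE) is defined as any untoward medical occurrence in a subject in the investigation". It asks for several separate assessments of each one: "AEs must be assessed for expectedness, severity, attribution (relatedness to the study intervention), and seriousness by the investigator". The SAE rule follows: "AEs deemed related to the intervention must be reported as serious adverse events (SAEs) if they become serious". The seriousness criteria (threat to life, death, longer hospital stay) appear only inside that sentence. The relatedness grades all refer to the study intervention, and the lowest positive grade needs little: "Possible: The AE may be related to the study intervention". The grade below it, unrelated, requires that the event clearly has no link to the intervention.

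Section 4.2 lists what is monitored. One item is "Other events classified as serious and unexpected", with no relatedness condition. The next covers other events that are fatal, serious or related, and there relatedness is to study procedures. Common complications of prematurity that do not count as AEs go to a Note to File. The 72-hour rule reads: "All deaths and serious adverse events SAEs that are at least possibly related and all unexpected SAEs will be reported".

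Section 5.3 names mortality to 36 weeks PMA, BPD and ROP as safety outcomes. It adds that the DSMC will look at other safety outcomes, "including all reported deaths and serious adverse events by treatment group", when considering whether to recommend suspension. Section 3.2.7 states that the trial is unmasked.

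**The concern.** A by-arm count of serious events is informative only if the rule for counting an event is the same in both arms. Relatedness to the intervention is not such a rule here, because one arm has no study algorithm to which an event could be attributed. The investigator or team member who makes the judgement is not described as masked.

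The error can run in two directions. A doubtful event in an algorithm infant is easily graded possible, while the same event in a control infant is easily graded unrelated, so the algorithm arm may show more SAEs with no true difference. Conversely, Sections 4.2 and 5.1 describe the risk as minimal. If staff therefore grade expected serious events as unrelated, a real excess in the algorithm arm would not appear among the reported SAEs. In either case the DSMC would be reading attribution practice as well as event rates.

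**Working it through.** The plan states no figure on this point, so the check is textual: follow each type of event through the three rules.

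| Event | 4.1 sentence | 72-hour rule, 4.2 | Monitoring list, 4.2 |
|---|---|---|---|
| Death | addresses the related case | reported, any attribution | listed |
| Serious, unexpected, non-fatal | addresses the related case | reported, any attribution | listed |
| Serious, expected, non-fatal, at least possibly related | must be reported as SAE | reported | listed |
| Serious, expected, non-fatal, unrelated | no rule given | not reported | listed, if the *or* is taken literally |
| Common complication of prematurity not counted as an AE | outside | outside | Note to File |
| Hypo- or hypernatremia on two consecutive values | AE by laboratory value | reported if it meets the rule | listed |

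Three things follow.

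1. The sections conflict. Section 4.1 ties SAE reporting to relatedness and is silent on a serious event judged unrelated. The 4.2 list does not require relatedness. The 72-hour rule treats possibly related SAEs and unexpected SAEs as different groups, which makes sense only if an SAE can be unrelated.
2. The reference differs: the intervention in 4.1, study procedures in 4.2. This matters for controls, because the doubly labeled water procedure is done in all enrolled infants and the algorithm is not.
3. The rows that differ only by attribution are the third and fourth. Under 4.1 and the 72-hour rule, expected non-fatal serious events are reported or not according to the relatedness grade. Section 5.3 does not say which reporting stream feeds its by-arm table.

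The mechanism can be written down. With N infants per arm, p the risk of an event of this type and q the share judged related, the expected reported count is N × p × q. Equal p does not give equal counts if q differs by arm. If q is near 0 in both arms, the counts are near 0 whatever the difference in p.

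A limiting case shows how far the result depends on inputs that the documents do not give. Take N = 90 / 2 = 45, the same p in both arms, at most one event per infant, and q = 0 in controls (the extreme case):

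- p = 10%, q = 5%: expected 45 × 0.10 × 0.05 = 0.2 against 0; chance that the algorithm arm shows more = 1 − (1 − 0.005)^45 = 20%; two-sided Fisher p < 0.05 in 0% of trials.
- p = 20%, q = 25%: expected 45 × 0.20 × 0.25 = 2.25 against 0; chance of more = 1 − (1 − 0.05)^45 = 90%; Fisher p < 0.05 in 2.4%.
- p = 40%, q = 50%: expected 45 × 0.40 × 0.50 = 9.0 against 0; chance of more about 100%; Fisher p < 0.05 in 91%.

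If serious events are counted whatever their attribution, both arms expect 45 × p (4.5 to 18 events), and Fisher p < 0.05 occurs in 2% to 3% of trials. All values of p and q are assumptions. The Note-to-File exclusion may put the true p for this narrow category below the range shown.

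**The case against.** A reader of 4.1 alone might infer that an event is an SAE only if it is judged related. The text does not say so. It states when reporting is mandatory, and the sentence before it treats attribution and seriousness as separate assessments for every AE in any infant. Section 4.2 brings in deaths, serious unexpected events and, on its plain wording, serious events in general. This stands, and it is why the finding is a conflict between sections and not an established exclusion.

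A reader might also infer that control infants can have no related event, or that the whole SAE comparison is lopsided by design. Neither is supported. Control infants undergo the doubly labeled water procedure, to which 4.2 could relate an event, and most of what the DSMC reviews needs no attribution. Section 5.3 also allows the DSMC to request other outcomes, and it sets no numerical stopping rule on SAE counts.

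Nor does the problem reach Hypothesis 3. Section 2.1 frames that in terms of named morbidities, not SAE counts.

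What the objection does not remove is the fourth row of the table. The 4.2 monitoring list includes such an event, 4.1 gives no rule for it, and the 72-hour rule leaves it out. Two coordinators could follow the text faithfully and report different events.

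**Conclusion.** The concern holds in a limited form. Sections 4.1 and 4.2 disagree on whether an SAE depends on relatedness, and on what the event must be related to. If 4.1 and the 72-hour rule govern practice, reporting of one category depends on an unmasked judgement that favours the algorithm arm: serious, expected, non-fatal events that are not common complications of prematurity. For that category the comparison in 5.3 can be unequal under equal true risk, or can miss an excess judged unrelated.

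Mortality, unexpected SAEs, BPD, ROP and serum-sodium AEs stay comparable between arms. The likely direction, more reported SAEs with the algorithm, is plausible from the wording of the relatedness grades. The size cannot be derived from the documents: the limiting case runs from negligible to large depending wholly on assumed p and q, and it sets control attribution to zero. The change is worth making because it is cheap and the SAE table informs a possible suspension.

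**What to change.** - In 4.1, define an SAE by the seriousness criteria alone, applied identically in both arms. Keep the exclusion of common complications of prematurity and their Note to File.
- Align 4.2 with that definition, and use one reference for relatedness, stating whether it covers the algorithm, the doubly labeled water procedure or both.
- Use relatedness and expectedness only to decide which SAEs go to the DSMC chair within 72 hours.
- In 5.3, state that the by-arm table counts serious events of any attribution, and list related SAEs separately.

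The cost is a few sentences of protocol text and some additional SAE form entries. The retained exclusion limits their number. Sample size and efficacy analysis are unchanged.

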4.2 Adverse Event Monitoring and Reporting

Extremely preterm infants commonly have multiple clinical complications and laboratory abnormalities associated with prematurity. Those listed as secondary outcomes will be collected in the REDCap database and reviewed monthly by the Study Team.

Published data involving this population and at the dose of sodium supplementation to be provided in this study have not shown any harmful effects, including hypernatremia, suggesting

this risk is minimal [33, 43]. In this patient population per routine standard of care, serum [Na] concentrations are checked daily to several times/week on infants receiving majority of intake parenterally and twice weekly to weekly for infants receiving primarily enteral intake. As this is a pragmatic, unmasked study evaluating an algorithm to assist clinicians in preventing total body sodium deficiency, AE reporting will specifically focus on states of sodium inadequacy or excess, and any additional adverse event monitoring the DSMC requests.

Adverse event monitoring will include:

Hyponatremia: mild [Na] 134-130; moderate [Na] 129-125; severe [Na] <125 Hypernatremia: mild [Na] 146-150; moderate [Na] 151-155; severe [Na] >155

(To be considered an AE, 2 consecutive measurements of hyper/hyponatremia will be required to rule out laboratory measurement variation.)

Common complications of prematurity that are not considered AE's will be collected and included in a Note to File for each participant.

Other events classified as serious and unexpected

Other events resulting in death or classified as a Serious or Related (to study procedures). All SAEs and AEs reported during this study will be followed until resolution or until the investigator confirms that the AE/SAE has stabilized and no more follow-up is required.

All deaths and serious adverse events SAEs that are at least possibly related and all unexpected SAEs will be reported to the Chair of the DSMC within 72 hours of awareness. An initial SAE form must be as complete as possible, including details of the current serious adverse event, including an Investigator assessment of the causal relationship between the event and study procedures. Information not available at the time of the initial report must be documented on a follow-up SAE form.

All AEs/SAEs that meet IU HRPP Policy on Reportable Events will be reported to the IRB within 5 working days.

SECTION 5. SAFETY, DATA MANAGEMENT, AND ANALYTICAL PLAN

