3.2.4 Study Intervention

Infants randomized to the study algorithm will have their urine [Na] measured at 2 weeks of age and every 2 weeks thereafter until 36 weeks corrected age. They will receive additional sodium supplementation after the second week of life if their urine [Na] is below the level in the diagram on the following page:

Postnatal	2	3	4	5	6	7	8	9	10	11	12	13	14
age (weeks)													
GA (birth)													
25 wk	<50		<40		<40		<40		<40		<30		<30
26 - 29 6/7 wk	<40		<40		<40		<40		<30		<30		

- i. Values in table represent urine [Na], expressed as mEq/L, obtained every other week
- ii. If urine [Na] is below threshold value, initiate supplementation at 4 mEq/kg/d above current Na intake. Adjust supplementation weekly to account for weight gain
- iii. Increase supplementation by 2 mEq/kg/d at subsequent biweekly points if <urine [Na] goal. Urine [Na] should not be obtained within 48 hr of use of diuretic agent
- iv. Provide supplementation if serum [Na] ≤132 mEq/L regardless of urine [Na] unless there is evidence of acute fluid overload (significant increase in weight). Hyponatremia in presence of high urine [Na] likely represents a condition of severe urinary sodium loss leading to hyponatremia
- v. Continue supplementation unless serum [Na] >144 mEq/L

If serum [Na] 145 – 146 mEq/L; reduce sodium supplement by ½ and consider measuring serum [Na] on subsequent day

If serum [Na] ≥ 147 mEq/L; discontinue sodium supplementation

vi. Continuation of supplementation after 38 weeks postmenstrual age will be at the discretion of the clinical care team

Routes of sodium administration:

We will allow flexibility in how supplemental sodium is delivered since this is not standardized in usual care practices.

For infants receiving ≤80 ml/kg/d of enteral feedings: The designated amount of sodium supplementation will be added to parenteral fluids to be infused over 24 hours. Sodium may be provided as sodium chloride acetate/citrate/bicarbonate or any mixture thereof.

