3.2.7 Blinding/Masking

None. Though randomization will be concealed preventing allocation bias, it is impossible to blind caregivers or parents to the intervention. Interim results will be provided to the Data Safety Monitoring Committee (DSMC) with treatment assignments labeled only as group "A" and "B." We will record sodium and fluid intake as well as serum and urine sodium values in order to assess protocol compliance.

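### A sodium AE needs two consecutive abnormal values while the algorithm arm acts on one, so AE counts can miss transient abnormalities, possibly differently by arm

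*Combined protocol and SAP*

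**What the plan says.** Section 4.2 directs AE reporting mainly at sodium deficiency and excess. It grades both: "Hypernatremia: mild [Na] 146-150; moderate [Na] 151-155; severe [Na] >155" and "Hyponatremia: mild [Na] 134-130; moderate [Na] 129-125; severe [Na] <125". It then limits what counts: "2 consecutive measurements of hyper/hyponatremia will be required to rule out laboratory measurement variation". No interval between the two measurements is given.

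Section 3.2.4 sets serum-based actions for infants randomized to the algorithm. At 145–146 mEq/L the instruction is to "reduce sodium supplement by ½ and consider measuring serum [Na] on subsequent day". Above that: "If serum [Na] ≥ 147 mEq/L; discontinue sodium supplementation". Supplementation is given at 132 mEq/L or below unless there is acute fluid overload. None of these steps waits for a second value. The comparator is current practice, and no rule for a high or low value is written for it.

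Section 4.2 describes serum sodium as a standard-of-care test. It is done daily to several times a week in mainly parenterally fed infants, and twice weekly to weekly in mainly enterally fed infants. The Appendix has a weekly serum sodium row that is not limited to one arm. Section 3.2.7 says "We will record sodium and fluid intake as well as serum and urine sodium values", for the purpose of checking compliance.

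**The concern.** Section 5.1 names mild hypernatremia as the main risk of the study. The AE count is the only planned output that would show it by arm:

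- the secondary outcomes (3.2.9) contain no serum sodium measure;
- the analysis section (5.2.2) plans none;
- the safety outcomes named for the DSMC (5.3) are mortality, BPD and ROP.

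The two-value rule is meant to screen out laboratory error. It does that cleanly only if nothing changes between the two measurements. In the algorithm arm something does change, by protocol, after one value. A normal second value may then mean that the excess was real and was corrected, yet no sodium AE is recorded. The same applies at the low end, where one value at or below 132 starts supplementation. If the chance of a second abnormal value differs between arms, the AE comparison mixes the frequency of abnormal sodium with the way each arm manages and samples it.

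**Working it through.** The plan states no rate of sodium abnormality, so there is no figure to reproduce. The check has three parts.

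**1. Thresholds side by side (sections 3.2.4 and 4.2).**

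| Serum sodium, mEq/L | Algorithm-arm action on one value | AE status of one value |
|---|---|---|
| 145 | halve supplement | below AE range |
| 146 | halve supplement | mild; AE only if next value is also 146 or above |
| 147 or more | stop supplement | mild to severe; AE only if next value is also 146 or above |
| 133–134 | none from serum value | mild; AE only if next value is also 134 or below |
| 132 or less | supplement | mild to severe; AE only if next value is also 134 or below |

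Throughout the hypernatremia range, the algorithm acts at or before the first of the two values that an AE needs. A value of 147 or more that stops the supplement, followed by 145 or less, leaves no sodium AE. Read literally, the same holds for a value above 155 followed by a normal one.

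**2. How much an action between measurements can matter (assumed inputs).** Simulation: true sodium has mean 138 or 140 and SD 4, measurement error has SD 1, and values are rounded to whole numbers. The result is the probability that the second value is 146 or above, given that the first was. Each range covers the two means.

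| Fall in true level between measurements, mEq/L | True level otherwise unchanged | Correlation 0.8 between true levels |
|---|---|---|
| 0 | 0.70–0.76 | 0.41–0.50 |
| 1 | 0.49–0.56 | 0.28–0.37 |
| 2 | 0.29–0.36 | 0.19–0.25 |
| 4 | 0.08–0.12 | 0.06–0.10 |

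A fall of 2 mEq/L therefore removes half or more of the countable events (0.29/0.70 = 0.41 and 0.25/0.50 = 0.50 remain, at the two extremes). Natural variation alone also removes many, in either arm.

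**3. Effect on the comparison between arms (assumed inputs).** Counted AE risk = r × p, where r is the risk of a first value of 146 or above and p is the probability that the next value is too (persistence). Expected AEs = 45 × r × p, with 90/2 = 45 infants per arm. Control: r = 0.10, p = 0.60, giving 45 × 0.10 × 0.60 = 2.7.

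| Algorithm r | Algorithm p | Expected algorithm AEs | Single-value ratio | Ratio under two-value rule |
|---|---|---|---|---|
| 0.10 | 0.60 | 2.7 | 1.00 | 1.00 |
| 0.10 | 0.45 | 2.0 | 1.00 | 0.75 |
| 0.10 | 0.30 | 1.4 | 1.00 | 0.50 |
| 0.10 | 0.15 | 0.7 | 1.00 | 0.25 |
| 0.10 | 0.70 | 3.2 | 1.00 | 1.17 |
| 0.20 | 0.30 | 2.7 | 2.00 | 1.00 |
| 0.20 | 0.60 | 5.4 | 2.00 | 2.00 |

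Equal persistence leaves the ratio intact. Lower persistence in the algorithm arm shrinks it; higher persistence inflates it. The documents do not say which case applies.

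**The case against.** A reader might infer that hypernatremia will be undercounted in the algorithm arm specifically. The documents do not support that, for these reasons:

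- The two-value rule covers both arms, and having no written control rule does not mean control clinicians ignore one abnormal value. Section 2.2 says most neonatologists decide on supplementation from serum sodium. If both arms react alike, the loss is similar in both.
- The only arm-specific sampling instruction is to "consider measuring serum [Na] on subsequent day" at 145–146. An early recheck could catch a second high value that a later routine sample would miss, which pushes the count the other way.
- The reduce-or-stop rule is part of the strategy under test. If it shortens episodes, fewer sustained episodes is a genuine effect. What the rule loses is transient events.

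It would also be too strong to say that a single severe value can never be an AE. Section 4.2 does not require both values to share a grade, so 158 followed by 147 qualifies, and serious events have their own reporting route. An isolated severe value is lost only when the next is normal and no such route applies.

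The numbers are assumed, and may be high. Section 2.2 reports that no infant has had supplementation stopped for sodium above 144 since the algorithm was introduced. Taking the 40 infants of the 2016 cohort, zero events gives a two-sided 95% upper limit of 1 − 0.025^(1/40) = 8.8%. That is a different measure from any value of 146 or above, and the cohort had no 25-week infants. At 45 per arm, counts this small will not separate the arms statistically under either definition.

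Finally, serum values are recorded and the DSMC may ask for more, so the information is largely recoverable. All of this limits the claim. It does not remove the gap: nothing in the plan commits anyone to produce the single-value tables, and the AE counts alone cannot show whether the loss was equal.

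**Conclusion.** The point holds in a limited form. A two-value AE definition without a time window, beside single-value action in the algorithm arm, can leave transient hyper- or hyponatremia out of the AE counts, and may do so unequally. That follows from sections 3.2.4 and 4.2 alone. Size and direction are unknown: the ratios above (0.25 to 1.17 when the single-value risks are equal, and 1.00 in place of 2.00 in one case) rest wholly on assumed risks and persistence rates. No bias against or in favour of the algorithm arm is shown. The gap deserves closing because it concerns the main stated risk and the remedy is cheap. The added tables would be descriptive and would not support a formal test at this sample size.

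**What to change.** Keep the two-value rule for individual AE forms, and state the time window within which two values count as consecutive. For the final analysis and each DSMC look, also tabulate by arm:

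- infants with any single value in each protocol grade of hypo- and hypernatremia;
- the highest and lowest value per infant;
- the number of serum measurements per infant, so that unequal sampling can be seen and allowed for;
- the number of infants with supplementation reduced or stopped for high sodium.

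List isolated severe-grade values separately, or count them as AEs. The sponsor should confirm that every serum value is captured, since the Appendix row is weekly while routine sampling can be more frequent.

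Cost: a short addition to section 4.2 and one set of tables from data already collected. Some isolated laboratory errors will be counted, equally across arms only if sampling frequency is similar, and single-value and extreme-value counts rise with the number of tests. That is why the measurement count belongs in the same table. No treatment threshold changes.
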